Visit windows are the time period during which a subject should be examined. The date of visits during the BLINKlink Phase are scheduled based on the date of receiving the randomization assignment. All attempts should be made to examine the subject as early in the window as possible in case the subject needs to re-schedule to a later date. In order to facilitate coordination of scheduling and to set reminders, the next appointment should be made upon completion of the current appointment, even if it does not occur for six months. The visit windows during the BLINKlink Phase are shown in Table 34-2. Some subjects will complete all three visits, and some subjects will not complete any of the visits during the BLINKlink Phase.

Table 34-2: Visit windows for the BLINKlink Phase.

| Visit | Target Window (Day) | Acceptable Window (Days) |
|-------|---------------------|--------------------------|
| 10 | 1,275 | 1,245-1,305 |
| 11 | 1,455 | 1,425-1,485 |
| 12 | 1,635 | 1,605-1,665 |

Glasses

At the closeout of the BLINK Study, all subjects were to receive a prescription for glasses, but no materials. As an incentive to continue participation, subjects will continue to receive glasses at no or reduced cost at each annual visit, including Visit 9 of the BLINK Study.

If subjects lose or break their spectacle frames, new ones will be provided by the study if they are not covered by warranty. In addition, new spectacle lenses may be provided if a spectacle prescription is found to have changed ≥ -0.50 D or if it is deemed to be clinically necessary to improve vision.

Each clinic will provide free polycarbonate, single vision lenses. All frames less than \$150 retail are provided at no charge. If a frame worth more than \$150 retail is chosen, the subject pays the difference. For example, if a subject picks out a frame that retails for \$200, the subject pays \$50 for the pair of glasses. If a subject desires transitions lenses, clip-on sunglasses, or any other item that costs extra, the subject pays retail cost for the extra item(s).

Forms

All forms for the BLINKlink Phase will be provided in the Electronic Data Capture (EDC) system, except forms that are to be maintained solely at the clinic site for subject privacy reasons. After each electronic form is completed, it will be printed and placed in the subject's binder (Table 34-3).

Table 34-3: Forms used at each visit during the study.

| Forms | Completed by | Visits 10, 12 | Visit 11 |

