Furthermore, no study has conducted thorough measurements of the optics and shape the eye in order to determine how soft bifocal contact lenses may slow myopia progression. Measurement of peripheral defocus with the contact lens on the eye while looking at distance and near will provide a thorough assessment of the refractive error experienced by the eye. Comparison of the treatment effect between varying add powers of soft bifocal contact lens wearers and soft spherical wearers will determine whether the effect is primarily due to changes in eye shape or due to the contact lens itself. If greater peripheral defocus created by stronger add powers leads to differences in treatment effect, the contact lens is the primary determinant of myopia control, whereas if the relationship between peripheral defocus and myopia control is a greater determinant of myopia control than the amount of defocus, then eye shape is the primary determinant of myopia control. In addition to peripheral defocus, this three-year study will also examine the role of accommodative lag, pupil size, peripheral astigmatism, and the most myopic peripheral meridian in order to provide the most thorough assessment ever conducted of the optical profile and its effect on refractive error development.

Determining the role of peripheral defocus on the shape of the eye is also important for understanding how peripheral defocus may alter refractive error. Animal models indicate that hyperopic defocus results in longer eye lengths restricted to the corresponding retinal location. If this is the case in humans, peripheral myopic defocus produces slower peripheral growth than central growth. Comparing the change in both central and peripheral refractive error between soft bifocal and single vision contact lens wearers will help determine whether peripheral myopic defocus results in local changes in ocular shape or uniform changes in eye growth.

[figure not shown]
Data regarding whether greater peripheral myopic defocus slows myopia progression and how peripheral myopic defocus alters eye shape will provide crucial guidance toward optimizing the peripheral defocus signal in future contact lenses designed for myopia control and perhaps prevention of myopia onset. With a three-year randomized clinical trial of 294 myopic children between the ages of 7 and 11 years at baseline, we will accomplish the following specific aims:

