Sample size calculations are driven, in part, by the desired difference in spherical equivalent change between the three groups. This difference needs to be of a magnitude that is considered clinically relevant. Sample sizes are based upon the percent reduction in myopia progression between the two soft bifocal contact lens groups and the single vision contact lens group. Data used in the calculations are taken from the single vision contact lens group of the ACHIEVE Study, where the mean (\pm SD) myopia progression was $-1.29 \text{ D} \pm 0.71$ over three years (Walline et al., 2008). If we want to detect a 50% treatment effect (reducing the amount of myopia progression by roughly 0.65 D in the +2.50 D add group) and we estimate that the mean treatment effect for the +1.50 D add group is halfway between the single vision contact lenses and the +2.50 D add group (i.e., reducing myopia progression by 0.30 D in the second add), then the sample size required at 80% power is 24 per treatment group. Estimating the effect of the +1.25 D add group to be halfway between the two groups results in the largest sample size possible (a conservative estimate). Should we find that both adds have a similar effect, we will be more than adequately powered. If we look at a reduction of 0.50 D (a treatment effect of 40% in the highest add group), then the sample size is 40 per treatment group at 80% power. A 30% treatment effect (a reduction of about 0.40 D in the amount of myopia progression in the +2.50 D add group) yields a sample size of 62 subjects per treatment group.

Specific Aim 2: to determine whether peripheral defocus created by soft bifocal contact lenses is associated with myopia progression to test the hypothesis that peripheral myopic defocus slows myopia progression in children

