| Peripheral refractive error without CL (OD)* | X | | | | X |
| Axial length (OU)* | X | | | | X |
| Peripheral eye length (OD)* | X | | | | X |
| Aberrations with and without CL (OD)* | | | | | Visit 5 only |
| Peripheral defocus with CL (OD)* | X | | | | X |
| Intraocular pressure (OU)* | X | | | | X |
| Dilated fundus examination (OU)* | X | | | | X |
| Contact Information Form | X | | | | X |
| History Form | X | | | | |
| Myopia Risk Factor Form | X | | | | |
| PREP2 Form | | | X | X | X |
| CISS Form | X | | X | Visit 4 only | X |
| Contact Lens Form | | | X | X | X |
| Parent Compliance Form | | | X | X | X |
| Insertion, Removal, and Care Training | | X | | | |
| Length of visit (hours) | 2.0 to 2.5 | 1.0 | 0.75 | 0.75 | 2.0 |

■ = masked measure; CL = contact lens; * = cycloplegic; Acc = accommodative

At Visit 1, we will measure high contrast distance visual acuity with the manifest refraction to determine eligibility. We will also measure low contrast and near visual acuities with the manifest refraction to determine the subjects' best attainable visual acuity. We will also measure each of the visual acuity measures with habitual contact lenses and spherical over-refraction in place at Visits 3 through 9 in order to compare visual acuity, while controlling for myopia progression, across the three treatment modalities.

We will measure the axial length, peripheral refractive error without contact lens, peripheral eye length, peripheral defocus with contact lens at distance, peripheral defocus with contact lens at near, pupil size, and near phoria at Visits 1, 5, 7, and 9 to determine the peripheral optical profile and the growth of the eye. We will measure accommodative lag at Visit 3 to give subjects time to adapt to their contact lenses, and at Visits 5, 7, and 9. We will perform a slit lamp biomicroscopy examination at every visit.

Subjects will complete a PREP2 survey at Visits 3 through 9 to compare satisfaction with vision correction between soft bifocal and soft spherical contact lenses. Subjects will not complete the PREP2 at Visits 1 or 2 because they are not required to be wearing myopic correction at these visits. All subjects will complete a compliance survey at Visits 3 through 9 in order to determine whether compliance with contact lens is associated with myopia control effects or differs by treatment group.

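### The Chapter 3 rule lets a difference between add powers name the contact lens as the primary cause of myopia control, although no eye-shape quantity enters that test

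*Combined protocol and SAP*

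**What the plan says.** In the text of Chapter 3 leading into the list of aims, the plan says that comparing treatment effect across add powers and spherical lens wearers "will determine whether the effect is primarily due to changes in eye shape or due to the contact lens itself". A rule with two limbs follows.

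- **Lens limb.** If stronger adds, through greater defocus, give different results, this "leads to differences in treatment effect, the contact lens is the primary determinant of myopia control".
- **Eye-shape limb.** The alternative is that the way defocus relates to slowing, as the plan puts it, "is a greater determinant of myopia control than the amount of defocus, then eye shape is the primary determinant of myopia control".

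Neither limb has a test, metric, threshold or order of precedence. Chapter 5 plans three analyses: a repeated measures ANCOVA of spherical equivalent by lens group (Aim 1), correlation and linear regression of progression on peripheral defocus (Aim 2), and a repeated measures ANCOVA of relative peripheral refractive error (Aim 3). None is linked to the rule. The same part of Chapter 3 presents the defocus and eye-shape results as guidance for designing future lenses.

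**The concern.** The conclusion that one factor is primary compares two factors. The lens limb examines only one of them: its null hypothesis is that add power makes no difference. Rejecting that null leaves open whether eye shape matters more, less or not at all. A larger trial does not help, because more power only makes the answer to the add-power question more certain.

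The eye-shape limb is comparative, but two analysts could apply it to the same data and disagree. The limbs are also not exclusive. The adds can differ while eye shape is judged the stronger determinant, and the rule then names two primary determinants. At stake is the mechanism conclusion, not the efficacy comparison.

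**Working it through.** **1. Inputs.** Chapter 5 gives alpha 0.05 and power 80%. It also prints a beta of 0.10, but the stated sizes fit 80%. The SD of three-year progression is 0.71 D. The largest scenario is "reducing the amount of myopia progression by roughly 0.65 D in the +2.50 D add group". The +1.50 D effect is described as halfway, which is 0.325 D, but printed as "i.e., reducing myopia progression by 0.30 D in the second add". The gap between adds is therefore 0.65 − 0.325 = 0.325 D, or 0.65 − 0.30 = 0.35 D as printed. The 40% and 30% scenarios (0.50 D and 0.40 D) give halfway gaps of 0.25 D and 0.20 D. There are 98 children per arm, 89 evaluable per arm as targeted, and about 88 after 10% loss (98 × 0.9).

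**2. The plan's own figures.** For a three-group F-test, the noncentrality is λ = n·Σ(mᵢ − m̄)²/SD².

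- Means 0/0.30/0.65: the sum of squares is 0.2117, so at n = 24, λ = 24 × 0.2117/0.5041 = 10.08 and power is 80%.
- Means 0/0.25/0.50 need n = 40, and 0/0.20/0.40 need n = 62.

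The stated 24, 40 and 62 per group are reproduced.

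**3. Lens limb as a test between the two adds.** Chapter 3 names no test, so two-sided 0.05 is assumed. Power is approximately Φ(gap/(SD·√(2/n)) − 1.96). At n = 89, SD·√(2/n) = 0.71 × √(2/89) = 0.1064 D. For the 0.325 D gap, 0.325/0.1064 = 3.05, and Φ(1.09) = 0.863 (0.859 by noncentral t).

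| Gap between adds | Chance the limb is met, n = 88 to 98 |
|---|---|
| 0.35 D (50% effect, as printed) | 90–93% |
| 0.325 D (50% effect, halfway) | 86–89% |
| 0.25 D (40% effect) | 64–69% |
| 0.20 D (30% effect) | 46–50% |
| 0 (adds equal) | 5% |

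**4. Lens limb as the three-group F-test.** Chapter 3 also names spherical lens wearers. On this reading, at n = 89 the limb is met in 92.7%, 99.1% and 99.99% of trials for the 30%, 40% and 50% scenarios. The lowest value, at n = 88 in the 30% scenario, is 92.4%.

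**5. Does the rate respond to eye shape?** The formulas contain only the arm means, the SD and n. With total SD held at 0.71 D, the share of variance related to eye shape cancels out. Simulation at n = 89 agrees in two cases.

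- Eye shape related to progression equally in all arms (10%, 25% or 40% of within-arm variance): 86–87%, 64–65% and 46–47% at gaps of 0.325, 0.25 and 0.20 D.
- Eye shape modifying the benefit within the bifocal arms: about 86%, 64–66% and 46%.

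The documents give no figure for the role of eye shape, so these shares are assumptions.

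**6. Can both limbs hold?** Read the eye-shape limb, for illustration, as eye shape having the larger R² between the two bifocal arms. At a 0.325 D gap, the add explains (0.325/2)²/((0.325/2)² + 0.71²) = 0.0264/0.5305 = 5% of variance there. If eye shape explains 25–40% of within-arm variance, it has the larger R² in over 99% of trials. Both limbs then hold together in about 86% of trials at n = 89 and 89–90% at n = 98.

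**The case against.** The strongest reply is that Chapter 3 asks what causes the treatment effect, not what explains variance in progression. If eye shape acts equally in every arm, it adds nothing to the difference between arms, and naming the lens is then correct. This stands. A reader might infer from step 6 that the rule wrongly credits the lens in most trials, or that 86% should be compared with a nominal 5% error rate. The documents support neither. The 86% is ordinary power for a real gap in the most favourable scenario, and Chapter 3 sets no 5% test of whether the lens is primary. Nor is a lens conclusion close to assured: at the 30% effect, the two-add reading gives less than an even chance or about one. It would also be wrong to call the eye-shape limb a coin toss, because that requires no lens effect at all, whereas the rule presupposes myopia control to be explained.

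It is also fair that the rule has two limbs, that it mentions the spherical arm, and that it is rationale text which no Chapter 5 analysis applies. Chapter 31 requires a detailed analysis plan for each approved paper, so there is a place to settle the matter.

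None of this supplies the missing comparison. When eye shape modifies the benefit, which does concern the treatment effect, the lens limb is still met at the same rate. And Chapter 3 states that the comparison will determine the answer.

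**Conclusion.** The concern holds as a defect of inference. The lens limb answers whether add power matters, and the plan reads it as showing that the lens matters most. The eye-shape limb is undefined, the limbs can contradict each other, and no planned analysis resolves them.

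The rates are 46–93% for the two-add reading and about 92% to over 99.9% for the F-test reading. They rest on the plan's scenarios, an assumed two-sided 0.05 test and a fixed total SD. They show how often the limb would be met, not how often its conclusion would be wrong. The size of any misattribution cannot be given, because the documents do not say how far eye shape mediates or modifies the effect. The primary efficacy comparison is unaffected.

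**What to change.** 1. In Chapter 3, state that a difference between +1.50 D and +2.50 D shows an effect of add power. Delete the inference that the lens is then the primary determinant.
2. Prespecify one model of three-year progression containing randomised lens group, Visit 1 no-lens relative peripheral refraction and their interaction. Fix in advance which eccentricities form the shape measure. Report the interaction, that is, how the treatment effect varies with baseline shape, with a 95% CI.
3. Make no primary-determinant claim from the add comparison alone. Ranking the two factors by variance explained is not a substitute, because it ranks predictors of progression and not of the treatment effect.

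The cost is a wording change and one extra regression. Table 8-2 already schedules no-lens peripheral refraction at Visit 1 and cycloplegic autorefraction at baseline and annually, and Chapter 12 lists both as masked. The mechanism claim becomes more modest. As a guide to precision, with residual SD 0.71 D and 89 per arm, the difference in slope between two arms per SD of baseline shape has a standard error of about 0.71 × √(2/89) = 0.106 D, so the CI half-width is about 1.96 × 0.106 = 0.21 D. Baseline shape addresses effect modification only. It does not address changes in shape after randomisation, and the text should say so.

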- Specific Aim 1:** to compare the change in myopia between single vision contact lens wearers and soft bifocal contact lens wearers to test the hypothesis that soft bifocal contact lenses slow myopia progression in a dose-dependent manner in children,
- Specific Aim 2:** to determine whether peripheral defocus created by soft bifocal contact lenses is associated with myopia progression to test the hypothesis that peripheral myopic defocus slows myopia progression in children, and
- Specific Aim 3:** to determine whether changes in ocular shape differ between children wearing single vision and soft bifocal contact lenses to test the hypothesis that peripheral myopic defocus globally slows eye growth.

Chapter 4: Study Design

This is a multi-center, randomized clinical trial. Subjects will be randomly assigned to wear single vision contact lenses, soft bifocal contact lenses with a +1.50 D add, or soft bifocal contact lenses with a +2.50 D add for at least three years. Figure 4-1 illustrates the study schedule.

Figure 4-1: Flowchart illustrating the visit schedule and randomization.

Chapter 5: Sample Size

All sample size calculations were performed using PASS 2005 software using $\alpha = 0.05$ and $\beta = 0.10$ (power = 80%). Estimates of sample size were computed for each specific aim.

Specific Aim 1: to compare the change in myopia between single vision contact lens wearers and soft bifocal contact lens wearers to test the hypothesis that soft bifocal contact lenses slow myopia progression in a dose-dependent manner in children

Aim 1 is designed to compare myopia progression between two soft bifocal adds and single vision contact lens wearers using the mean value of the cycloplegic spherical equivalent (sphere + $\frac{1}{2}$ cylinder) as measured at one, two, and three years. These comparisons will be made using the common estimate of error obtained from a three group x three time point repeated measures analysis of covariance (ANCOVA), with the baseline spherical equivalent used as a covariate. To increase the efficiency of the F-tests performed as part of the ANCOVA, the total sample size will be equally allocated between the soft bifocal and single vision contact lens groups.

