Analysis of the relationship between the amount of peripheral defocus and the amount of myopia progression will provide information on how the level of peripheral defocus may affect the progression of myopia. That is, are higher levels of peripheral myopic defocus associated with a decreased rate of foveal myopia progression? Peripheral defocus is measured in this study at multiple locations (20°, 30°, and 40°) in two gaze positions (nasal and temporal). The association between peripheral defocus and myopia progression will be assessed using a correlation analysis and linear regression. Based on recent work by Sankaridurg et al. (2011), a clinically meaningful magnitude of correlation between peripheral defocus and myopia progression is 0.25. To detect a correlation as small as 0.25 at 80% power would require 123 subjects total.

Specific Aim 3: to determine whether changes in ocular shape differ between children wearing single vision and soft bifocal contact lenses to test the hypothesis that peripheral myopic defocus globally slows eye growth

Aim 3 is designed to evaluate differences in the change in ocular shape between the two soft bifocal and single vision contact lens groups using the measure of relative peripheral refractive error across the horizontal and vertical meridians of the eye. Relative peripheral refractive error is computed by subtracting the central cycloplegic spherical equivalent autorefraction from the peripheral spherical equivalent autorefraction, each measured with no refractive

error correction. Analyses will use a repeated measures ANCOVA with gaze direction and fixation as within-subject factors. To increase the efficiency of the F-tests performed as part of the ANCOVA, the total sample size will be equally allocated between the soft bifocal and single vision contact lens groups.

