Sample size estimates are based upon a magnitude difference of the change in “ocular shape” between the single vision contact lens and the +2.50 D add bifocal treatment groups of 0.40 D. In order to ensure that we have adequate sample size to find a true difference, we have made the assumption that the +1.50 D add bifocal group will experience a change that is intermediate between the other two groups (i.e., 0.20 D). Making this assumption gives us a conservative estimate of sample size (i.e., the maximum sample size). While no longitudinal data assessing the amount of change in periphery that can be considered clinically meaningful, it is reasonable to assume that a clinically meaningful change in the center would be considered a clinically meaningful change in the periphery as well. As such, we know that the minimal difference in central refractive error change that has been detected in previous studies is 0.13 D over one year. If this amount of difference in refractive error change continues for three years, then the minimal meaningful difference would be 0.39 D, which we rounded to a 0.40 D difference. The standard deviation arises from the Study of Theories about Myopia Progression, and is set at 0.85, which represents the most conservative standard deviation in the change in relative peripheral refraction seen across measures. Using this information the sample size required to detect this magnitude of difference in the change in ocular shape between treatment groups with 80% power is 89 subjects per group, for a total sample size of 267 subjects.

Sample Size Conclusion

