Table 5-1 provides a summary of the sample size requirements based on the three study aims. Although we strive to retain all subjects, the sample size will be adjusted to account for a possible 10% loss to follow-up. This is a reasonable expectation. [name], when at Ohio State, had a retention rate of 98% in his Study of Theories about Myopia Progression clinical trial, and other clinical vision studies conducted at the University of Houston have retention rates exceeding 90%. Likewise, [name] experiences at Ohio State with ACHIEVE (OSU clinic saw 100% of subjects for final visit) and the Contact Lens and Myopia Progression trial (100% of subjects at final visit) indicate that a 10% loss to follow-up is an acceptable assumption. Using the maximum sample size from Table 5-1 (n=267) and adjusting for 10% loss to follow-up gives a **total sample required of 294** (98 children assigned to each treatment group).

Table 5-1: Total sample size required at 80% power in the Soft Bifocal Contact Lens Myopia Control Study

| Aim | Total sample |
|----------------------|--------------|
| Specific Aim 1 | |
| 50% treatment effect | 72 |
| 40% treatment effect | 120 |
| 30% treatment effect | 186 |
| Specific Aim 2 | 123 |
| Specific Aim 3 | 267 |

Chapter 6: Timeline

During the first six months of funding, preparation for the trial will begin. The DSMC will meet as early as possible (after preparation of study forms and DSMC binders) in order to finalize the protocol. Once the protocol is finalized, certification of examiners will begin at the FIG meeting, both near the end of the initial six-month period.

Recruitment will begin at the beginning of month seven and continue for 15 months. All follow-up visits will begin within one week of the first subject visit. The last one-year, two-year, and three-year visits are expected to be complete within one month of the anniversary date of the last subject enrolled.

The DSMC will meet annually, after recruitment and each year of follow-up is complete and the data are analyzed. FIG meetings will be held after each DSMC meeting in order to update protocols, motivate investigators, and discuss problems encountered. Writing groups will also meet during the FIG meetings.

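### Chapter 5 pairs beta of 0.10 with 80% power (it should read 0.20), and 294 enrolled covers 9.2% loss, not 10%, if 267 are to remain

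*Combined protocol and SAP*

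**What the plan says.** The opening paragraph of Chapter 5 states that every calculation was made in PASS 2005 with alpha of 0.05 and "\beta = 0.10$ (power = 80"%). The rest of the chapter uses 80% only:

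- Aim 1: "then the sample size required at 80% power is 24 per treatment group" for the 50% effect, with 40 and 62 per group for the 40% and 30% effects.
- Aim 2: "To detect a correlation as small as 0.25 at 80% power would require 123 subjects total".
- Aim 3: "with 80% power is 89 subjects per group, for a total sample size of 267 subjects".
- The table's title: "Table 5-1: Total sample size required at 80% power in the Soft Bifocal Contact Lens Myopia Control Study".

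The Sample Size Conclusion then takes the largest of these: "Using the maximum sample size from Table 5-1 (n=267) and adjusting for 10% loss to follow-up gives a total sample required of 294", that is, 98 per group.

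**The concern.** A beta of 0.10 means 90% power and a power of 80% means a beta of 0.20, so the opening sentence contradicts itself. Because it governs the whole chapter, a reader who trusts the beta would think the trial was designed for 90% power. On that reading Aim 3 would need 116 per group, or 348 evaluable children, which is more than the 294 to be enrolled.

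The second point concerns what the 10% is taken of. Children are lost from those enrolled, so an allowance that leaves 267 has to be worked from the enrolled number. Adding 10% to the evaluable number gives a slightly smaller total. What is at stake is whether the documented justification of the trial's size is true as written.

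**Working it through.** **Inputs, all from Chapter 5.** Alpha 0.05. Aim 1: SD 0.71 D; reductions of 0.30 and 0.65 D in the two add groups (50% effect), 0.50 D in the higher add (40%) and 0.40 D (30%), with the middle group taken as halfway in the last two. Aim 2: correlation 0.25. Aim 3: SD 0.85 D; differences of 0.20 and 0.40 D. Equal allocation to three groups.

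**Assumed methods.** The PASS procedures are not named. For Aims 1 and 3 I used a one-way three-group F-test, with noncentrality lambda = n x sum of (group mean - overall mean)² / SD² on 2 and 3(n - 1) degrees of freedom. For Aim 2 I used a two-sided Fisher z test.

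**Step 1: which power was used?** For Aim 3 the deviations from the overall mean are -0.20, 0 and +0.20, so their squares sum to 0.08 and lambda = 89 x 0.08 / 0.7225 = 9.85. Power is 80.47%. For Aim 2, n = ((1.960 + 0.842) / atanh(0.25))² + 3 = 123.3. All five stated sizes:

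| Calculation | Stated size | Power at that size | Implied beta | Size for 90% power |
|---|---|---|---|---|
| Aim 1, 50% effect | 24 per group | 80.05% | 0.200 | 32 per group |
| Aim 1, 40% effect | 40 per group | 80.14% | 0.199 | 53 per group |
| Aim 1, 30% effect | 62 per group | 80.19% | 0.198 | 81 per group |
| Aim 2 | 123 in total | 79.90% | 0.201 | 164 to 165 in total |
| Aim 3 | 89 per group | 80.47% | 0.195 | 116 per group |

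Every stated size sits at 80%. None is near its 90% counterpart.

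**Step 2: the total of 294.**

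- The plan's figure: 267 x 1.10 = 293.7, rounded up to 294 (98 per group).
- The number that leaves 267 after 10% loss: 267 / (1 - 0.10) = 296.7, rounded up to 297 (99 per group).
- The loss that 294 can absorb: 1 - 267/294 = 27/294 = 9.18%.
- What 294 leaves after 10% loss: 294 x 0.90 = 264.6, or 98 x 0.90 = 88.2 per group. In whole children, 88 per group and 264 in all, 3 fewer than 267 (about 1%).

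**Step 3: does the shortfall matter?** At 88 per group:

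- Aim 3: 79.99% (80.09% if 88.2 is used unrounded), against 80.47% at 89.
- Aim 1: 92.5%, 99.0% and over 99.9% for the 30%, 40% and 50% effects. Its largest requirement is 186 in total.
- Aim 2, at 264 in total: 98.5%.

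**The case against.** The beta contradiction has no real defence: the line is legible and nothing elsewhere in the manual corrects it. The case on the other side concerns the loss allowance, the weight given to it, and how much the reproduction proves.

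- *Adding 10% is a common shortcut, and 294 is correct arithmetic under it.* True of the arithmetic. But Chapter 5 presents 267 as the number required and the 10% as loss to follow-up. The shortcut does not leave 267 after a 10% loss among those enrolled.
- *Power is unaffected.* This stands. 294 still gives Aim 3 80% power to rounding at 10% loss. The 9.2% limit protects the count of 267, not the power target. The plan also calls the 10% only a possibility and cites retention of 98%, above 90% and 100%. Under Chapter 9 (Discontinuation), a child who stops but agrees to return for Visit 9 is not counted as lost.
- *Other figures are rounded just as loosely.* Also fair. Aim 2 strictly needs 124, since 123.3 rounds up. In Aim 1, an exact halfway value of 0.325 D gives 79.97% at 24, so 25 would be needed. Taking exactly 30% of 1.29 D (0.387 D) instead of the rounded 0.40 D would need 66 per group. None of this brings a stated size near 90% power, and it confirms that these are points of exactness.
- *The planned analyses for Aims 1 and 3 are repeated measures ANCOVA, not a one-way F-test.* This stands as a limit. The check shows which power the authors used; it does not certify that the sizes suit the planned models.

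**Conclusion.** Both figures are wrong as written, and both are minor. Beta should read 0.20. That rests on the definition of power, on the 80% repeated throughout the chapter, and on five sizes that reproduce at 79.9% to 80.5% power under the assumed F-test and a two-sided Fisher z test. No sample size follows from the erroneous beta, so none changes.

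The total of 294 covers 9.2% loss if 267 children are to be evaluable. At the stated 10% the shortfall is about 3 children, and Aim 3 power remains 80% to rounding. Aim 1, which carries the primary outcome of cycloplegic autorefraction, is unaffected, as is Aim 2. Neither point is a reason to doubt that the trial is large enough for its stated aims.

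**What to change.** In the opening paragraph of Chapter 5, change beta from 0.10 to 0.20. In the Sample Size Conclusion, say that enrolling 294 leaves 267 evaluable with losses of up to 9.2%, and that at 10% loss about 264 remain, with Aim 3 power of about 80.0%. It would help to name the PASS procedures used, so that the sizes can be checked directly.

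The cost is one symbol and one sentence. The only thing given up is the nominal loss allowance, which falls from 10% to 9.2%. Enrolment should not be reopened: the manual is Version 1.8, dated 5/31/18. Table 6-2 planned recruitment to end in July 2015. Even the longer course in Chapter 34, with about 20 months between the first and last subject and a first enrolment around 10/14 in Figure 34-1, puts the end near mid-2016.
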